4.3. Analysis Set

4.3.1. Informed Consent (ICF)

The ICF will include all patients who provide informed consent, including screen failures.

4.3.2. Full-analysis set (FAS)

The FAS will include all randomized participants who receive at least 1 drop of study drug. The FAS will be the primary population used for the efficacy analyses. All analyses using the FAS will group participants according to initial randomized treatment.

4.3.3. Safety set

The Safety set will include all participants who receive any amount of study drug (SYD-101 0.01%, SYD-101 0.03%, or Vehicle). The Safety set will be the primary population used for safety analyses. Treatment assignment will be based on the treatment actually received. Participants who receive one incorrect treatment kit but whose treatment is corrected to their randomized treatment at the next treatment dispensation will be included in all analyses as receiving the correct treatment.

4.3.4. Per-protocol analysis set (PPS)

The PPS will include all participants in the FAS who do not have any major protocol deviations and have at least 1 post baseline measurement for SE. The PPS will be defined separately for the Month 24, Month 36 and Month 48 analyses. Major protocol deviations will be identified prior to database lock and breaking the study mask at Month 24. Additional visits and/or participants may be excluded from the PPS at Months 36 and Month 48 based on review of accumulating

deviations. Efficacy endpoints analyzed for the PPS are to be treated as a sensitivity analysis. Treatment assignment will be based on the treatment actually received.

4.3.5. Special Subsets

The SYD-101 Efficacy Subset will include all participants in the FAS who were randomized to one of the two active treatment arms and stay on active treatment for the entire 48-month study.

The Vehicle to Escape Efficacy Subset will include all participants in the FAS who were randomized to one of the two active treatment arms, were re-randomized to vehicle at Month 36, and initiated escape medication before Month 48.

For the EMA Submission, additional special subsets are defined based on refractive histories of participants prior to enrollment. Refractive history was required for participants presenting with myopia (SE) of < 0.75 D and requested of all other participants, if available. The refractive history will be used to calculate annual progression rate for three intervals.

- First Refraction History Date (RH1) to Screening
- Second Refraction History Date (RH2) to Screening (if two historical refractions are available)
- RH1 to RH2 (if two historical refractions are available, the earlier history will be considered RH1)

For each interval, the annual progression rate will be calculated as the change in SE divided by the number of days (later date – earlier date + 1) and multiplied by 365.25 to obtain an annual progression rate for that interval. Using the annual progression rates calculated for the intervals above, the following 2 subsets below are defined and the study annual progression rate will be analyzed for these subgroups as secondary endpoints for EMA only.

- Fast Progressor Subgroup 1: This subgroup will include all randomized participants in the FAS. With refractive history of ≥ 0.50 D progression/year for any of the three history time intervals. Intervals of less than 28 days will not be included as they can overestimate a progression rate. It is expected to have approximately 250 randomized participants meeting this criterion.
- Fast Progressor Subgroup 2: This subgroup will include all randomized participants in the FAS with refractive history of ≥ 0.75 D progression/year for any of the three history time intervals. Intervals of less than 28 days will not be included as they can overestimate a progression rate. It is expected to have approximately 200 randomized participants meeting this criterion.

5. Participant Disposition

5.1. Disposition

Two separate disposition summaries will be provided:

A disposition of participants includes the number and percentage of participants for the following categories: participants who signed informed consent/assent, participants randomized, participants randomized by region and country, participants in the Safety analysis set, participants in the FAS, participants in PPS, participants who completed Month 24 and Month 36 visits, participants who completed the study, participants who discontinued from the study, participants who discontinued from the study treatment, and participants who received escape medication. Additional disposition summaries will be provided for subgroups such as Age, Sex, Race and Iris Color.

A separate summary will be provided for randomized withdrawal period and will contain counts and percentages of participants in the following categories:

- Those initially assigned to the SYD-101 0.01% arm (not on escape medication) will be re-randomized in a 1:1 ratio to receive either masked SYD-101 0.01% or Vehicle
- Those initially assigned to the SYD-101 0.03% arm (not on escape medication) will be re-randomized in a 1:1 ratio to receive either masked SYD-101 0.03% or Vehicle
- Those initially assigned to the Vehicle arm (not on escape medication) will be re-assigned to receive masked SYD-101 0.03%

All percentages will be based on the number of FAS participants. Disposition data will be listed as well.

5.2. Protocol Deviations

Protocol deviations will be tracked by the clinical team on an ongoing basis based on the Protocol Deviations Rules document. The Protocol Deviation Rules document includes a description of identified potential deviations and assigns a rule number, deviation type (ICH/GCP Deviation vs. Protocol Deviation), deviation subtype (inclusion/exclusion criteria, visit scheduling, missing doses, treatment compliance, etc.), deviation type (efficacy vs. safety), significance (Significant vs. Non-Significant), deviation source (Medical Monitor Review, Site Monitoring, Automated Data Checks, etc.) and severity (Include Participant in All Analyses, Exclude Participant from PPS, Exclude efficacy assessments after date of deviation, Exclude efficacy assessment on the date of deviation, etc.) for each deviation. The Study Deviations Rules document may be updated as the study is ongoing and new deviations are identified. Each approved version of the Study Deviations Rules document will be maintained in the clinical project files.

Major protocol deviations are defined as the subset of deviations which are considered to have potential significant impact on analysis and results in the exclusion of a participant's data from analysis. Major protocol deviations that may be considered include, but are not limited to the following:

- Failure to fulfill any of the important inclusion/exclusion criteria
- Significant deviations in dosing adherence
- Taking prohibited medication or treatment listed in protocol Section 6.5.1
- Significant deviations in autorefraction process (e.g., only one autorefraction measurement taken per eye)

Participants with major protocol deviations will be tabulated by deviation sub-type for each treatment group. All percentages will be based on the number of FAS participants. Additionally, all major and minor deviations will be listed for all FAS participants.

6. Demographics and Baseline Characteristics

6.1. Demographics and Baseline Disease Characteristics

Demographic and baseline characteristics variables, including age (years), age category (3 years to <6 years, 6 years to <9 years, 9 years to <12 years, and 12 years to 14 years), sex, height, weight, ethnicity, race, region (Europe and US), degree of parental myopia (Mild, Moderate, High, Unknown), degree of parental myopia (presented separately for mother and father), baseline SE (average of right and left eyes), baseline SE category (0.50 D to 3.0 D and >3.0 D to 6.0 D), participants with myopia (SE) < 0.75 D, participants with myopia (SE) \geq 1.0 D, annual progression rate prior to baseline, participants with history of myopia progression of at least 0.5 D and at least 1.0 D in the past 12 months, axial length (average of right and left eyes), best-corrected visual acuity (BCVA) using ETDRS letters (average of right and left eyes), Binocular Near-BCVA (logMAR), pupil diameter (average of right and left eyes), intraocular pressure (IOP) (average of right and left eyes), corneal endothelial cell count (average of right and left eyes), iris color category by patient, average time outdoors category (<= Median or > Median) and average time near work category (<= Median or > Median) will be summarized by treatment group, as well as demographic groups such as Age, Sex, Race and Iris Color, and over all participants combined for the Safety set, FAS, and PPS, and optionally for Special Subgroups (Section 4.3.5). Age, height, weight, baseline SE, annual progression rate prior to baseline, axial length, BCVA, near binocular BCVA, pupil diameter, IOP, and corneal endothelial cell count will be summarized using descriptive statistics. Age categories, sex, ethnicity, region, race, and degree of parental myopia, baseline SE category, participants with myopia history, iris color category and activities categories (time near work and time outdoors) will be summarized with the number and percentage of participants in each parameter category.

Age will be calculated as (date of informed consent – date of birth)/365.25.

The annual progression rate prior to baseline will be calculated is noted in Section 4.3.5 for the interval between RH1 and Screening.

A participant will be considered to have a history of progression of at least 0.5 D in the past 12 months if the difference between the SE at the earliest historical refraction performed within 365 days prior and the SE at the screening/baseline refraction is at least a 0.5 D progression. Similarly, a participant is considered to have a history of progression of at least 1.0 D in the past 12 months if the difference between the SE at the earliest historical refraction performed within 365 days prior and the SE at the screening/baseline refraction is at least a 1.0 D progression.

Iris color will be summarized at the participant level. Blue, green, grey, and hazel eyes will be categorized as light. Eyes that are black, brown, or other will be categorized as dark. If a

participant has different colored eyes, the participant will be classified as having dark eyes if either eye is dark.

Participant demographic and baseline characteristics will be presented in a listing.

6.2. Medical History

Medical histories are captured on the eCRF and the investigator will record verbatim term, location (ocular or non-ocular, OD/OS/OU for ocular), start date, and stop date or indication of ongoing. Medical history will be coded using the Medical Dictionary for Regulatory Activities (MedDRA, Version 21.1 or higher). The number and percentage of participants with any history will be reported by treatment group. Additionally, medical history will be summarized by the number and percentage of participants with medical history by MedDRA System Organ Class and Preferred Term (PT) by treatment group.

Medical histories will be summarized separately for ocular and non-ocular histories. For ocular summaries, participants will be counted at a given level (any medical history, by System Organ Class, and by PT) if the participant has a history reported in at least one eye.

Percentages will be calculated based on number of participants in the Safety set. Also, by-participant listings of medical histories will be presented.

6.3. Inclusion and Exclusion Criteria

Prior to randomization, the investigator will assess whether the participant fulfills all of the inclusion and exclusion criteria outlined in the protocol. If a participant does not fulfill all of the requirements, the specific inclusion criterion not met or exclusion criterion which was met will be recorded on the eCRF and presented in a data listing.

7. Treatments and Medications

All concurrent medications (prescription, over-the-counter, and supplements), adjunct therapies, and concurrent procedures will be recorded on the appropriate eCRF page. Collection of medications and procedures will begin at Screening and include any medications used within 30 days will be recorded in the eCRF. Any changes in concomitant medications also will be recorded in the participant's eCRF. Medications will be coded with the World Health Organization Drug (WHODrug) Dictionary, which will be updated throughout the life of the study.

7.1. Prior and Concomitant Medications

Prior medications are defined as those which are taken prior to the initiation of study treatment. This includes medications which start prior to Day 1 but continue while the participant is on study treatment.

Concomitant medications are defined as those medications which are taken on or after the initiation of study treatment (Day 1). This includes medications which start prior to Day 1 but continue while the participant is on study treatment.

Prior and concomitant medications will be summarized separately by presenting the total number of medications and the number and percentages of participant with at least one medication will be summarized by treatment group. The number and percentages of medications will also be summarized by treatment group and by ATC level 1 term, ATC level 2 term, and preferred term for the Safety set.

Prior and concomitant medications will be summarized separately for ocular and non-ocular medications. For ocular summaries, participants will be counted at a given level (any medication, by ATC level, and by PT) if the participant has a medication reported in at least one eye.

All medications will be presented in data listings with an indicator to identify whether their use is prior and /or concomitant.

7.2. Concurrent Procedures

Details regarding concurrent procedures will be listed.

7.3. Study Treatments

The active study treatment, SYD-101, is a sterile topical ophthalmic solution of atropine sulfate. The Vehicle (control) treatment formulation is identical to SYD-101, except that it does not contain active drug (atropine sulfate) and H₂O is used instead of D₂O. SYD-101 and Vehicle are clear ophthalmic solutions packaged in identical white, 5-mL low-density polyethylene (LDPE) ophthalmic bottles. Each night at bedtime, 1 drop of assigned study drug is to be instilled in each eye.

7.3.1. Extent of Exposure

Overall duration of exposure to any study treatment is defined as the total number of days a participant is exposed to any study drug (active SYP-101 or Vehicle) during the 48 month treatment period and will be presented as the total number of days from the first dose (Day 1) to the last dose date as recorded on the EOS/ET page: (last dose date - date of first dose + 1). If the last dose date on the EOS/ET page is missing, or if a participant is lost to follow-up, the latest available visit date will be used.

Overall duration of exposure to any study treatment will be calculated at Month 24 and Month 36 as follows: (date of Month 24 [or Month 36] visit - date of Day 1 visit +1).

Additionally, participants may change study treatment due to receipt of escape medication or re-randomization at Month 36. See Table 7-1 below for potential patterns of changes to study drug doses over time (not including early discontinuations of study therapy.) Duration of exposure for

each specific treatment for each participant will be calculated as Date of Last Dose for given treatment arm – Date of First Dose for given treatment arm + 1. The start date of escape medication will be the date of the first visit where the participant's end of visit status is marked as "Continuing on Rescue Medication". The date of re-randomization at Month 36 will be used as the last dose date for SYD-101 treatment for SYD-101 0.01% and SYD-101 0.03% arm participants who are re-randomized to vehicle as well as the first dose for vehicle treatment for these participants. For the SYD-101 0.03% treatment arm, participants who are re-randomized to vehicle at Month 36 can receive SYD-101 0.03% in two non-consecutive time courses (from Baseline to Month 36 and from escape after re-randomization to Vehicle at Month 36 to Month 48), the duration of exposure for the two treatment courses will be summed to calculate the total exposure to SYD-101 0.03%.

Table 7-1 Potential Patterns of Dose Changes

Randomized Treatment	Treatment Period		Randomized Withdrawal	
	Baseline to Month 24	Month 24 to Month 36	Month 36 to 42	Month 42 to 48
SYD-101 0.01%	SYD-101 0.01%	SYD-101 0.01%	SYD-101 0.01%	SYD-101 0.01%
	SYD-101 0.01%	SYD-101 0.01%	SYD-101 0.01%	SYD-101 0.03% escape
	SYD-101 0.01%	SYD-101 0.01%	Vehicle	Vehicle
	SYD-101 0.01%	SYD-101 0.01%	Vehicle	SYD-101 0.03% escape
	SYD-101 0.01%	SYD-101 0.03% escape	SYD-101 0.03% escape	SYD-101 0.03% escape
SYD-101 0.03%	SYD-101 0.03%	SYD-101 0.03%	SYD-101 0.03%	SYD-101 0.03%
	SYD-101 0.03%	SYD-101 0.03%	SYD-101 0.03%	SYD-101 0.03% escape
	SYD-101 0.03%	SYD-101 0.03%	Vehicle	SYD-101 0.03% escape
	SYD-101 0.03%	SYD-101 0.03%	Vehicle	Vehicle
	SYD-101 0.03%	SYD-101 0.03% escape	SYD-101 0.03% escape	SYD-101 0.03% escape
Vehicle	Vehicle	Vehicle	SYD-101 0.03%	SYD-101 0.03%
	Vehicle	SYD-101 0.03% escape	SYD-101 0.03% escape	SYD-101 0.03% escape

Descriptive statistics including the number of participants, mean, SD, median, minimum, and maximum for the study treatment exposure will be summarized for overall exposure to any study drug, exposure for each treatment regardless of initial randomized treatment, and exposure to each treatment by initial randomized treatment group using the Safety analysis set. The durations of exposure and study participation will then be classified into one of the following categories: <= 91 days, 92 to 182 days, 183 to 280 days, 281 to 364 days, 365 to 546 days, 547 to 728 days, 729 to 910 days, 911 to 1092 days, 1093 to 1274 days, 1275 to 1456 days, and >=

1456 days and will be presented as the number and percentage of participants in each duration category. Summary tables for subgroups (Age, Sex, Race and Iris Color) will be created as well.

In addition, a summary table showing the number of participants on each treatment per visit will be included, up to 48 months.

Participant treatment status (continuing on masked medication and continuing on escape medication) will be collected at each visit and data will be presented in a listing.

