7 STUDY DRUG DISCONTINUATION AND PARTICIPANT DISCONTINUATION OR WITHDRAWAL FROM STUDY

7.1 DISCONTINUATION OF STUDY DRUG

Discontinuation from study drug does not mean discontinuation from the study, and remaining study procedures should be completed as indicated by the study protocol. If a clinically significant finding is identified (including, but not limited to changes from baseline) after enrollment, the investigator or qualified designee will determine if any change in participant management is needed. Any new clinically relevant finding will be reported as an AE.

The data to be collected at the time of study intervention discontinuation will include the procedures as listed in the schedule of activities.

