9.2 SAMPLE SIZE DETERMINATION

[figure not shown]
Group sample sizes of 280 in each treatment arm will achieve at least 90% power to detect a difference in the percentage of participants with myopic progression (>0.75 D) of at least 15% between a SYD-101 arm and Vehicle. Power calculations presented in Figure 9-1 are based on the Chi-squared test at a 2-sided significance level of 0.025.

Figure 9-1: Power for 2-Sided Chi-Square Test Evaluated at Alpha=0.025 for Proportion Responders When 280 Participants Per Arm

Additionally, group sample sizes of 280 per treatment arm achieves >90% power to detect a reduction of 0.18 D or more in the annual progression rate between SYD-101 and Vehicle, assuming a common SD of 0.60 D. Power calculations presented in Figure 9-2 are based on a 2-sample t-test evaluated at the 0.025 significance level.

Figure 9-2: Power for 2-Sided T-Test Evaluated at Alpha=0.025 for Annual Progression Rate When 280 Participants Per Arm

Calculations were performed using SAS® 9.3 Software (SAS Institute, Inc, Cary, North Carolina).

This study plans to continue follow-up for all enrolled participants through Month 48, regardless of early discontinuation of study treatment or receipt of escape medication/prohibited therapy. All participants will be included in analyses based on their observed data. Because the effect size estimates have already taken into consideration the impact of no therapy/escape medication, enrollment of additional participants beyond 280 participants per treatment arm has not been planned.

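### Overall exposure at the Month 24 and Month 36 analyses is computed from visit dates, so children who stop study drug but keep attending are counted as fully exposed

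*SAP*

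**What the plan says.** SAP 7.3.1 (Extent of Exposure) contains three rules.

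- **Overall exposure, 48-month period.** This is the "total number of days from the first dose (Day 1) to the last dose date as recorded on the EOS/ET page". A fallback covers missing information: "If the last dose date on the EOS/ET page is missing, or if a participant is lost to follow-up, the latest available visit date" is then used.
- **Overall exposure at the two earlier analyses.** The same quantity gets its own formula here, namely "date of Month 24 [or Month 36] visit - date of Day 1 visit +1". This rule has no last-dose term and no provision for a child without the visit, and it does not refer back to the fallback.
- **Exposure to each treatment.** This is "Date of Last Dose for given treatment arm – Date of First Dose for given treatment arm + 1".

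Durations are summarised on the Safety set, placed in categories that start at 91 days or less, and repeated by age, sex, race and iris colour.

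The protocol separates stopping drug from leaving the study. Section 7.1 says "Discontinuation from study drug does not mean discontinuation from the study" and asks that the remaining procedures be completed. Section 9.2 plans follow-up through Month 48 "regardless of early discontinuation of study treatment or receipt of escape medication/prohibited therapy".

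**The concern.** The Month 24 and Month 36 analyses support the EU and US submissions. At both, the plan's overall measure of how long children were treated would in fact measure how long they were followed. The two differ for exactly the children whom the protocol asks sites to retain: those who stop drops and keep attending. Their overall exposure is overstated, and it contradicts the last-dose definitions on either side of it in the same section.

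A second gap concerns children who leave early. With no Month 24 or Month 36 visit date the formula has no input, so as written these children drop out of the summary and only the longer durations remain.

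What is at stake is the accuracy of the overall exposure summary and its subgroup versions in the two submission analyses. No hypothesis test depends on it.

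**Working it through.** The plan states no exposure total that could be reproduced. The check therefore applies the rule literally and then sizes its effect.

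**Inputs.** Month 24 is week 104 and Month 36 is week 156 (Protocol 1.3): 104 × 7 = 728 days and 156 × 7 = 1092 days. There are 280 participants per arm (SAP 4.1). The simulations in SAP 4.1 assume a 7% annual rate that combines dropout and treatment discontinuation. The split between the two is not given.

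**One child.** Last dose on day 182, attending on target:

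| Analysis | Month 24/36 overall rule | Per-treatment rule | Excess |
|---|---|---|---|
| Month 24 | 728 | 182 | 546 |
| Month 36 | 1092 | 182 | 910 |

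If the same child leaves the study instead, the overall formula returns nothing, while last dose minus first dose plus 1 still gives 182.

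**Duration categories.** SAP Table 4-1 puts the Month 24 analysis window at days 683 to 773. Taking the Month 24 visit as the one in that window, every literal overall value falls in the 547–728 or 729–910 day category, and all shorter categories are empty by construction. The wider primary-endpoint window (638 to 773) gives the same result. At Month 36 (1047 to 1137), only 911–1092 and 1093–1274 can be filled.

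**Effect on the mean.** Assume a constant stopping hazard h = −ln(1 − 0.07) = 0.0726 per year, and let T be the target day divided by 365.25.

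- Share stopped by T: 1 − exp(−hT).
- True mean exposure in days: 365.25 × (1 − exp(−hT)) / h.

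| | Month 24 | Month 36 |
|---|---|---|
| Share stopped or left | 13.5% (about 38 of 280) | 19.5% (about 55 of 280) |
| True mean, days | 677.8 | 981.7 |
| Mean from the SAP rule, days | 728 | 1092 |
| Overstatement | 50.2 days (50.2/677.8 = 7.4%) | 110.3 days (110.3/981.7 = 11.2%) |
| Mean true exposure among stoppers, days | 355 | 526 |

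The rule's mean is 728 (or 1092) if all stoppers keep attending. It is the same if they all leave and are omitted, because only children with the visit then contribute.

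**Range.** With an assumed annual rate of 3% to 10% in place of 7%, the overstatement is 3.1% to 10.9% at Month 24 and 4.6% to 16.6% at Month 36, on the same terms.

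**If leavers receive their last-dose date.** Only stoppers who stay then add error. Assume that stoppers and leavers share the same timing. If half stay, the excess at Month 24 is 0.5 × 50.2 = 25 days (3.7%). If a quarter stay, it is 0.25 × 50.2 = 13 days (1.9%). These splits are assumptions.

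**The case against.** The strongest reply is that a reader might infer that the plan hides early stopping, or masks a tolerability difference between 0.01%, 0.03% and Vehicle. The documents do not support that reading. Stopping is still reported by arm in the disposition summary (SAP 5.1), in per-treatment exposure by initial randomised group and in the count of participants on each treatment at each visit (SAP 7.3.1). It also appears in the summaries of adverse events leading to drug withdrawal or discontinuation (SAP 9.1, 9.1.1, 9.1.5). Adverse event percentages use participant counts, and no exposure-adjusted rate is planned. Nothing in the documents shows that the error would differ by arm. All of this stands and limits the point to the overall exposure summaries.

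A second reply is that the Month 24/36 formula is meant only for children still in the study, with the preceding last-dose and latest-visit rules covering those who left. The short duration categories suggest such an intention, and Protocol 7.2 asks for an early-termination visit. It would therefore go too far to say that leavers will certainly have no value; that is the literal result only. But the SAP does not carry those rules over, and doing so would not correct children who stop drug and keep attending.

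A third reply is that the last dose may not be recorded at the lock for a child still in follow-up. The end-of-study page does not yet exist, drug-withdrawn records capture only stops due to adverse events, and clinic visits after Month 6 are six months apart. This is a fair limit on how exactly a stop can be dated. It does not justify treating the visit date as the last dose.

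**Conclusion.** The point holds as an error in a stated derivation rule. Followed as written, SAP 7.3.1 gives wrong overall exposure for children who stop drug but keep attending, at both submission analyses, and conflicts with the 48-month and per-treatment definitions beside it. The missing rule for children without the visit is an ambiguity to be closed.

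The 50-day and 110-day figures are upper bounds under the SAP's combined 7% rate. They also assume a constant hazard and visits on target, and they fall if early leavers are given their last-dose date. The consequence is confined to descriptive overall exposure, including its subgroup tables. The efficacy analyses and type I error are untouched.

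**What to change.** In SAP 7.3.1, replace the Month 24/36 formula, for every Safety-set participant, with:

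min(last dose date, Month 24 [36] visit date) − first dose date + 1,

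using the participant's analysis cut-off under SAP Section 4 in place of the visit date when no visit falls in the window. A child still on drug at the visit keeps the visit date as the end point. Use the same last dose date in the per-treatment rows, so that the two measures agree.

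State the fallback for a child who has stopped but has no last dose date at the lock: the drug-withdrawn record first, otherwise an approximation from the treatment status collected at each visit. Say that this approximation can be off by up to one visit interval (26 × 7 = 182 days after Month 6) and that, if taken from the last visit marked as continuing, it tends to understate exposure. Report time in study as a separate line; SAP 7.3.1 already mentions study participation alongside exposure.

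The cost is one SAP sentence plus the fallback, and a programming change. Reported mean overall exposure will be slightly lower.
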